8.2 Study-Specific Adverse Event Capture

8.2.1 Duration and Grade of Adverse Event Capture

All grade 3 and 4 adverse events occurring after the subject has taken the first dose of study drug until the end of study will be recorded in the subject's case record form.

Documentation must be supported by an entry in the subject's file. A laboratory test abnormality considered clinically relevant, e.g., causing the subject to withdraw from the study, requiring treatment or causing apparent clinical manifestations, or judged relevant by the Investigator, should be reported as an adverse event. Each grade 3 or 4 event should be described in detail along with start and stop dates, severity, relationship to investigational product, action taken and outcome.

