The randomized, phase III study in STS subjects provided a key comparison of safety with pazopanib compared to placebo.[34] The most common AEs reported in $\geq 20\%$ of subjects in the pazopanib arm were fatigue (65%), diarrhea (59%), nausea (56%), weight decreased (51%), hypertension (42%), anorexia (40%), hair color change (depigmentation; 39%), and vomiting (34%), tumor pain (30%), dysguesia (28%), gastrointestinal pain (24%), headache (23%), musculoskeletal pain (23%), myalgia (23%), and dyspnea (20%). Most of the events were grade 1 or 2. A higher number of grade 3 AEs were reported in the pazopanib arm (63%) compared with the placebo arm (28%). The most frequent grade 3 AEs in the pazopanib arm were increased alanine aminotransferase (ALT), increased aspartate aminotransferase (AST), hypertension, and diarrhea. The frequency of grade 4 and grade 5 AEs was similar between the pazopanib and placebo arms: grade 4 in 7% and 6%, respectively; grade 5 in 4% and 3%, respectively.

When pazopanib was compared with sunitinib in 1102 subjects (554 subjects taking pazopanib and 548 subjects taking sunitinib), the frequency of AEs was similar (>99% in both). The safety profiles observed between the treatment arms were different, with greater frequency of diarrhea (63% pazopanib, 57% sunitinib) and hypertension (47% pazopanib, 41% sunitinib). Subjects who took pazopanib when compared with subjects taking sunitinib experienced lower frequency of fatigue, nausea, dysguesia and palmar-plantar erythrodysesthesia (PPE) syndrome. Grade 3 and 4 reported adverse events were similar between treatment arms, adding no comparative risk. However, grade 3 AEs of increased

ALT; increased ASP and headache occurred more frequently in the pazopanib arm when compared with the sunitinib arm. [34]

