A complete physical examination will be performed at Screening, including height. A symptom-directed physical examination including weight will be performed at all other visits unless indicated otherwise. Clinically significant physical examination findings after the administration of the first day of dosing will be recorded as adverse events.

12-lead Electrocardiogram (ECG)

A resting 12-lead ECG will be performed at the Screening Visit, unless performed for standard of care within 14 days. The investigator or a designee will sign and date the ECGs, determine if any findings outside normal physiological variation are clinically significant (in consultation with a cardiologist if necessary), and document this on the ECG report. ECGs will also be performed at the initiation of pazopanib maintenance therapy, Cycle 1 Day 1 and Cycle 2 Day 2.

Vital Signs

Vital sign determinations of heart rate, blood pressure and body temperature will be measured at all visits unless indicated otherwise.

Pregnancy Test

For female subjects of childbearing potential, a serum pregnancy test will be performed at the Screening Visit and a urine pregnancy test will be done at the Run-in period Day 1 visit prior to the first dose of pazopanib versus placebo. Subjects considered not of childbearing potential must be documented as being surgically sterile or post-menopausal (for at least 1 year). The test results must be reviewed and determined to be negative prior to dosing. If the urine pregnancy test is positive at Cycle 1 Day 1, it should be confirmed by a serum pregnancy test. The test may be repeated at the discretion of the Investigator at any time during the study. Should the subject become pregnant or suspect she is pregnant while participating in this study, she should inform the Investigator immediately. The Principal Investigator should be notified and will be responsible for contacting the representative at Novartis.

Clinical Laboratory Tests

All subjects will undergo the laboratory assessments outlined in **Appendix A**. After Cycle 1 Day 1, clinical laboratory tests should be performed within 72 hours surrounding the scheduled study visit date. Any laboratory value outside the reference range that is considered clinically significant by the investigator will be followed as appropriate. Clinically significant laboratory values will be recorded as adverse events if they meet the criteria as specified in **Section 7.7**.

Tumor Assessments (Radiologic)

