SAEs will be sent to Novartis as they arise in subjects exposed to pazobanib using copies of the original Case Report Form pages and within 24 hours of first becoming aware of the event, regardless of causality assessments.

Pregnancy Reports

Reports of pregnancy information on any female subjects who becomes pregnant while participating in the study and following exposure to the study product will be sent to Novartis using copies of the original Case Report Form pages and within two weeks of the pregnancy (including premature termination of the pregnancy).

Information on the status of the mother and child will be reported to the coordinating center. Generally, follow-up will be requested by Novartis no longer than 8 weeks following the estimated delivery date.

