Descriptive displays of preliminary clinical endpoints (pathologic response, progression-free survival, overall survival) will compare response for the pazopanib and placebo groups, and will investigate the relationship between early pharmacodynamic response (by PET) and clinical endpoints. Response of high-risk soft tissue sarcoma to neoadjuvant chemoradiation therapy was estimated as 52% (38% no residual tumor, 14% ≥ 95 pathologic necrosis) in a series of 496 patients.[9] A smaller series found only 13/46 (28%) with $< 10\%$ viable tumor in surgical specimens following a variety of neoadjuvant regimens.[51] To direct planning of future studies, we will measure the rate of complete pathological response defined as greater than 95% necrosis in the surgical excision specimen. A 90% Wilson (score) binomial confidence interval will be computed for the rate of complete pathological response.

There are no stopping rules planned for toxicity, but safety will be monitored continuously. All subjects who are registered and receive at least one dose of study drug will be included in the safety analysis.

All reported adverse events will be coded using the Cancer Therapy Evaluation Program (CTEP) Common Toxicity Criteria version 4.0. The number and percent of subjects reporting adverse events (all, severe or worse, serious and related) will be quantified. Listings will be provided for all on-study deaths and adverse events that lead to withdrawal from study. Narratives of all serious adverse events and deaths on-study will be provided.

Correlative study assays will be analyzed using descriptive statistics, generally comparing pazopanib and placebo groups. Correlation will also be evaluated between pazopanib trough concentrations and drug exposure over the dosing interval (area-under-the-concentration-curve, AUC) in subjects consenting to the full intensive pharmacokinetic visits.

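### Section 8.2.1 captures only grades 3 and 4 systematically, so the count of *all* adverse events planned in Section 14.1 would be incomplete

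*Combined protocol and SAP*

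**What the plan says.** Section 8.2.1 sets the capture rule by grade: "All grade 3 and 4 adverse events occurring after the subject has taken the first dose of study drug until the end of study" go into the case record form. It asks for detail at the same level: "Each grade 3 or 4 event should be described in detail along with start and stop dates, severity, relationship to investigational product", together with action taken and outcome.

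Section 14.1 sets the output: "The number and percent of subjects reporting adverse events (all, severe or worse, serious and related) will be quantified". It also plans listings of deaths and of events leading to withdrawal, and narratives of serious events. On coding it says: "All reported adverse events will be coded using the Cancer Therapy Evaluation Program (CTEP) Common Toxicity Criteria version 4.0".

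Some routes into the record carry no grade limit:

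- Laboratory findings (Section 8.2.1): "A laboratory test abnormality considered clinically relevant, e.g., causing the subject to withdraw from the study, requiring treatment", among other reasons, are to be reported. Section 4.3 adds a second laboratory rule that points to the criteria in Section 7.7.
- Examination findings (Section 4.3): "Clinically significant physical examination findings after the administration of the first day of dosing will be recorded as adverse events".
- Serious events (Section 8.1): "SAEs will be sent to Novartis as they arise in subjects exposed to pazobanib using copies of the original Case Report Form pages". Seriousness, not grade, is the test.
- Blood pressure (Appendix F): readings at each assessment and, for treatment-emergent hypertension, grade changes, symptoms and drugs.

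Safety of the pazopanib and chemotherapy sequence is a secondary objective (Section 3.2).

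**The concern.** A row for *all* adverse events, kept apart from a row for *severe or worse*, has a clear meaning only if lower grades are collected in the same way for every patient. Section 8.2.1 does not ask for that. A reader of the final report would take *all* to mean any grade, and would be looking at grade 3 and 4 events plus whatever lower-grade events happened to qualify by another route.

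This touches a stated secondary objective. The comparison of pazopanib with placebo rests on 14 days of dosing, and tolerability over so short a period is likely to show mainly in lower-grade symptoms. For the cited phase III sarcoma trial, Section 2.4 reports fatigue in 65%, diarrhea in 59% and nausea in 56% of the pazopanib arm, and says of the events overall: "Most of the events were grade 1 or 2".

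Lower grades also act on study drug. Table 1 in Section 7.7.1 interrupts it for grade 1 hemoptysis, holds it for grade 2 palmar-plantar erythrodysesthesia, interrupts it for other clinically significant grade 2 events, and stops it for grade 2 pulmonary or non-hemorrhoidal gastrointestinal bleeding. The grade rule in Section 8.2.1 requires none of these on the form.

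**Working it through.** The plan states no figure on this point, so there is none to reproduce. The check sets each category in Section 14.1 against what the capture rules deliver. I read *severe or worse* as grade 3 or higher, which the plan does not spell out.

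| Category in 14.1 | Source under the plan | Can it be produced? |
|---|---|---|
| All | Grades 3 and 4 complete (8.2.1); lower grades only by the laboratory, examination, blood pressure or serious-event routes | Not as an any-grade count |
| Severe or worse | Grades 3 and 4 (8.2.1); grade 5 from the serious event form required for deaths (7.8) | Yes |
| Serious | Captured by seriousness (8.1) | Yes |
| Related | Relationship required for grade 3 or 4 events (8.2.1) | For grade 3 or 4 and serious events; not for all grades |
| Death listing | Serious event form (7.8) | Yes |

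The wording on serious and related events can be read as one category or two. If it is one, the *related* row raises no separate problem. If it is two, an all-grade *related* count is unsupported.

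**Direction of the error.** Events can only be missing from the *all* row, so it can only understate any-grade incidence. The missing events are mainly non-serious grade 1 or 2 symptoms that yield no laboratory or examination finding.

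**Size, as an illustration only.** With 2:1 allocation of 21 patients, 14 receive pazopanib and 7 placebo. Section 2.4 gives grade 3 events as 63% on pazopanib and 28% on placebo in the sarcoma trial, read here as percentages of patients. It gives any adverse event in more than 99% of patients in a separate comparison with sunitinib.

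- Pazopanib, grade 3: 0.63 × 14 = 8.8, about 9 patients.
- Pazopanib, any grade: 0.99 × 14 = 13.9, about 14 patients.
- Placebo, grade 3: 0.28 × 7 = 2.0, about 2 patients.

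The gap on pazopanib is about 14 − 9 = 5 patients. The rates come from two different trials, not from a 14-day run-in, and they leave out doxorubicin and ifosfamide. They show direction and nothing more.

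**Link to evaluability.** Section 7.8 removes patients with less than 80% of the intended dose from the primary endpoints. If the intended pazopanib dose is taken as the 14-day run-in, two missed days leave 12/14 = 86% and three leave 11/14 = 79%. A short interruption for a lower-grade symptom could therefore take a patient out of the primary analysis without Section 8.2.1 requiring that event to be recorded. Section 14.1 nevertheless intends to examine why data are missing.

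**The case against.** The strongest reply is that grade 3 and 4 capture is a deliberate choice in a 21-patient pilot. On that view Section 14.1 refers to reported events, so *all* means all events the protocol collects. Recording every grade through inpatient doxorubicin and ifosfamide would also be a real burden. Much of this stands: the restriction is a legitimate choice, and capture through every cycle is not needed. But on this reading the row has no stable content, because its lower-grade part depends on investigator judgement and on the type of finding. The label would have to say so.

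A reader might also infer more than the documents support:

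- *That the whole safety table fails.* It does not. The severe and serious counts and the death listing can be produced.
- *That nothing below grade 3 is recorded.* The laboratory, examination, blood pressure and serious-event routes have no grade floor. The *all* and *severe* rows need not be nearly identical.
- *That deaths are lost because Section 8.2.1 does not name grade 5.* Section 7.8 puts them on a serious event form within 24 hours, and Section 14.1 lists them.
- *That most hypertension goes unrecorded.* Appendix F covers it.
- *That the run-in is the only blinded period.* Section 6.0 keeps the blind until surgery. What is confined to 14 days is placebo-controlled dosing.
- *That dose interruptions cannot be traced to a cause.* Many can. Laboratory triggers and visible skin changes can enter under Section 4.3, Table 1 asks for the cause of bleeding to be documented, withdrawal reasons go on the form (Section 7.8), and dose modifications are reviewed bi-monthly (Section 9.2). The gap is narrower: a temporary interruption for a non-serious, lower-grade symptom has no required adverse event record.

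**Conclusion.** The two sections conflict on one category. Followed as written, *all* adverse events would be complete for grades 3 and 4 and unsystematic below that, so it would understate any-grade incidence. An all-grade *related* count has the same defect. The rest of the planned safety output holds.

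The size of the shortfall cannot be derived from the documents. Over the full preoperative course, chemotherapy toxicity may bring the number of patients with at least one event close to the total under either rule. The loss would then show mainly in run-in results and in counts by type of event. The conclusion assumes that *severe or worse* means grade 3 or higher and that no separate form instructions widen the capture rule. It deserves correction because safety is a secondary objective, and the correction is cheap.

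**What to change.** Reconcile Sections 8.2.1 and 14.1 in one of two ways.

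1. **Change the label.** In Section 14.1, replace *all* with a category such as *grade 3 or higher, plus serious and other protocol-reportable events*, and limit any *related* count to the same set. The cost is a line of wording and a less inclusive table.
2. **Change the capture.** In Section 8.2.1, record all grades, with relationship and action taken, from first dose at least through the end-of-week-two assessment. Also record any event of any grade that interrupts, reduces or stops pazopanib or placebo. In Section 14.1, state the period to which the all-grade count applies. Appendix A already schedules a toxicity assessment at the end of week two, so the cost is modest extra data entry for 21 patients.

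Under either option, name grade 5 in Section 8.2.1 for tidiness and bring the laboratory reporting rules in Sections 4.3 and 8.2.1 into line. Neither option alters how patients are treated.

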8.2.2 Adverse Event Grading

Toxicities will be graded using the NCI Common Terminology Criteria for Adverse Events (CTCAE) (the most current version available. The scale in its entirety can be found at:

http://evs.nci.nih.gov/ftp1/CTCAE/CTCAE_4.03_2010-06-14_QuickReference_8.5x11.pdf

9.0 DATA AND SAFETY MONITORING PLAN

9.1 Data Monitoring

Data and safety monitoring for the study will be performed by the Clinical Research Support Office of the Fred Hutchinson/University of Washington Cancer Consortium (the “Consortium”). The purpose of the monitoring is to verify the accuracy of the study data, assess compliance with the protocol and with Good Clinical Practice (GCP) regulations, and assure the timely and complete reporting of safety (adverse event) data. To facilitate the monitoring, medical records for subjects enrolled by the University of Washington/Seattle Cancer Care Alliance (the coordinating center) and Oregon Health & Science University will be reviewed by the Clinical Research Support Office. The records will be made available for monitoring by study staff.

Monitoring for this study will be scheduled in accordance with the Cancer Consortium Data and Safety Monitoring Plan. The intervals and scope are detailed in the monitoring plan.

9.2 Safety Monitoring

Investigators will conduct continuous review of data and patient safety. Bi-monthly review meetings will include Principal Investigators and study coordinators. Other study staff may be included per the PI’s discretion. A summary of the following will be presented at each meeting:

- Total subject accrual
- Significant toxicities experienced by enrolled subjects
- Dose modifications and responses

The Principal Investigators and co-Investigators will provide study oversight and will review adverse events for trends that indicate a change in the known risks to the study participant. The Principal Investigator will meet with these individuals on a regular basis to review recently acquired data, and adverse events. If it is the opinion of any investigator that the risks or benefits to a patient warrant suspension or termination of study activity, the recommendation must be submitted in writing to the Principal Investigator for safety committee review. The safety committee will include [name], and [name] in addition to the Principal Investigators and primary study staff. Suspension or termination of study activities may also be initiated based on the bi-monthly review.

9.3 Auditing

All trials conducted or coordinated by UW/SCCA are subject to audit. Internal audit reports will be reviewed at bi-monthly meetings.

9.4 Quality Assurance Review (QAR)

All trials conducted or coordinated by UW/SCCA are subject to quality assurance review (QAR). Quality assurance review reports will be reviewed at bi-monthly meetings.

The CTEP Comprehensive Adverse Event and Potential Risks list (CAEPR) provides a single list of reported and/or potential adverse events (AE) associated with pazopanib. A subset, the Agent Specific Adverse Event List (ASAEL), appears in a separate column and is identified with **bold** and *italicized* text. This subset of AEs (ASAEL) contains events that are considered 'expected' for expedited reporting purposes only.

Version 2.2, March 18, 2010¹

Adverse Events with Possible Relationship to Pazopanib (GW786034) (CTCAE 4 Term) [n= 1019]			EXPECTED AEs FOR ADEERS REPORTING Agent Specific Adverse Event List (ASAEL)
Likely (>20%)	Less Likely (<=20%)	Rare but Serious (<3%)	Expected
CARDIAC DISORDERS			
Chest pain			Angina
Bradycardia			Bradycardia
QT-prolongation			
	Cardiac dysfunction		
		Left ventricular systolic dysfunction	
		Myocardial infarction	
ENDOCRINE DISORDERS			

	Hypothyroidism		
		Liver Failure	
GASTROINTESTINAL DISORDERS			
	Abdominal pain		Abdominal pain
	Constipation		
	Flatulence		
Diarrhea			Diarrhea
		Gastrointestinal fistula ²	Gastrointestinal fistula²
		Gastrointestinal hemorrhage ³	
		Gastrointestinal perforation ⁴	Gastrointestinal perforation⁴
Nausea			Nausea
Vomiting			Vomiting
Dyspepsia		Pancreatitis	Pancreatitis
GENERAL DISORDERS AND ADMINISTRATION SITE CONDITIONS			
Fatigue			Fatigue
Chills/Rigors		Vital organ hemorrhages	
		Infection	

INVESTIGATIONS			
	Alanine aminotransferase increased		Alanine aminotransferase increased
	Aspartate aminotransferase increased		Aspartate aminotransferase increased
	Blood bilirubin increased		Blood bilirubin increased
	Gamma-glutamyl transpeptidase increased		GGT Increased
		Electrocardiogram QTc interval prolonged (accompanied by Torsades de pointes)	
	Lipase increased		
Lymphocyte count decreased			Leukopenia
	Neutrophil count decreased		Neutropenia
Platelet count decreased			Thrombocytopenia
	Serum amylase increased		
	Weight loss		
METABOLISM AND NUTRITION DISORDERS			
Anorexia			Anorexia
	Dehydration		Dehydration
Hyperglycemia			Hyperglycemia
	Hypermagnesemia		

Hypoglycemia			Hypoglycemia
	Hypomagnesemia		
	Hypophosphatemia		Hypophosphatemia
Weight Loss			
MUSCULOSKELETAL AND CONNECTIVE TISSUE DISORDERS			
Arthralgia			Arthralgia
Myalgia			
NEOPLASMS BENIGN, MALIGNANT AND UNSPECIFIED (INCL CYSTS AND POLYPS)			
	Tumor pain		
NERVOUS SYSTEM DISORDERS			
	Dizziness		Dizziness
Dysgeusia			
	Extrapyramidal disorder		
	Headache		Headache
		Stroke	Aneurysm
		Reversible posterior leukoencephalopathy syndrome	
RENAL AND URINARY DISORDERS			
Hematuria			
Proteinuria			Proteinuria
		Urinary fistula	Urinary fistula
REPRODUCTIVE SYSTEM AND BREAST DISORDERS			
		Female genital tract fistula	Female genital tract fistula
		Uterine fistula	Uterine fistula
		Vaginal fistula	Vaginal fistula
RESPIRATORY, THORACIC AND MEDIASTINAL DISORDERS			
Cough			
Dyspnea			
	Respiratory hemorrhage ⁵		Respiratory hemorrhage⁵
Oral stomatitis			Mouth sores
Dysphonia			Hoarseness
	Pneumothorax		
SKIN AND SUBCUTANEOUS TISSUE DISORDERS			
	Alopecia		Alopecia
Edema in face, hands, ankles, feet and/or eyelids			
Desquamation			
Hemoptysis			
Blurred vision			Ametropia
	Palmar-plantar erythrodysesthesia syndrome		
Rash maculo-papular			Rash maculo-papular
Skin hypopigmentation			Skin hypopigmentation
VASCULAR DISORDERS			

Hypertension		Hypertension
	Thromboembolic event (venous) ⁶	
		Thrombotic microangiopathy (including thrombotic thrombocytopenic purpura and hemolytic uremic syndrome)
		Vital organ hemorrhage
		Vascular disorders – other (arterial thromboembolic event) ⁶

¹This table will be updated as the toxicity profile of the agent is revised. Updates will be distributed to all Principal Investigators at the time of revision. The current version can be obtained by contacting [contact].

²Gastrointestinal fistula includes Anal fistula, Colonic fistula, Duodenal fistula, Esophageal fistula, Gastric fistula, Gastrointestinal fistula, Ileal fistula, Jejunal fistula, Oral cavity fistula, Pancreatic fistula, Rectal fistula, and Salivary gland fistula under the GASTROINTESTINAL DISORDERS SOC.

³Gastrointestinal hemorrhage includes Anal hemorrhage, Cecal hemorrhage, Colonic hemorrhage, Duodenal hemorrhage, Esophageal hemorrhage, Esophageal varices hemorrhage, Gastric hemorrhage, Hemorrhoidal hemorrhage, Ileal hemorrhage, Intra-abdominal hemorrhage, Jejunal hemorrhage, Lower gastrointestinal hemorrhage, Oral hemorrhage, Pancreatic hemorrhage, Rectal hemorrhage, Retroperitoneal hemorrhage, and Upper gastrointestinal hemorrhage under the GASTROINTESTINAL DISORDERS SOC.

⁴Gastrointestinal perforation includes Colonic perforation, Duodenal perforation, Esophageal perforation, Gastric perforation, Ileal perforation, Jejunal perforation, Rectal perforation, and Small intestinal perforation under the GASTROINTESTINAL DISORDERS SOC.

⁵Respiratory hemorrhage includes Bronchopulmonary hemorrhage, Epistaxis, Laryngeal hemorrhage, Mediastinal hemorrhage, Pharyngeal hemorrhage, and Pleural hemorrhage under the RESPIRATORY, THORACIC AND MEDIASTINAL DISORDERS SOC.

⁶These events can result in life-threatening pulmonary, cardiac, cerebral, and other complications.

